8.4.3.2 RELATIONSHIP TO STUDY INTERVENTION

All adverse events (AEs) must have their relationship to study intervention assessed by the clinician who examines and evaluates the participant based on temporal relationship and his/her clinical judgment. Investigators are to judge the causal relationship of the event with the study intervention as "suspected", "unsuspected" or "unknown".

8.4.3.3 EXPECTEDNESS

The Sponsor will be responsible for determining whether an adverse event (AE) is expected or unexpected. An AE will be considered unexpected if the nature, severity, or frequency of the event is not consistent with the risk information previously described for the study intervention.

8.4.4 TIME PERIOD AND FREQUENCY FOR EVENT ASSESSMENT AND FOLLOW-UP

The occurrence of an adverse event (AE) or serious adverse event (SAE) may come to the attention of study personnel during study visits and interviews of a study participant presenting for medical care, or upon review by a study monitor.

All AEs including local and systemic reactions will be captured on the eCRF. Information to be collected includes event description, time of onset, clinician's assessment of severity, relationship to study product (assessed only by those with the training and authority to make a diagnosis), and time of resolution/stabilization of the event. All AEs occurring while on study must be documented appropriately regardless of relationship. All AEs will be followed to adequate resolution.

Any medical condition that is present at the time that the participant is screened will be considered as baseline and not reported as an AE. However, if the study participant's condition deteriorates at any time during the study, it will be recorded as an AE.

Changes in the severity of an AE will be documented to allow an assessment of the duration of the event at each level of severity. AEs characterized as intermittent require documentation of onset and duration of each episode.

The investigator will record all reportable events with onset dates occurring any time after informed consent is obtained until 7 (for non-serious AEs) or 30 days (for SAEs) after the last day of study participation. At each study visit, the investigator will inquire about the occurrence of AE/SAEs since the previous visit. Events will be followed for outcome information until resolution or stabilization.

8.4.5 ADVERSE EVENT REPORTING

All identified non-serious AEs (related and unrelated) must be recorded and described on the eCRF.

8.4.6 SERIOUS ADVERSE EVENT REPORTING

Every Serious Adverse Event (SAE), regardless of suspected causality, occurring after the subject has provided informed consent and until at least 30 days after the subject has stopped study treatment must be reported to the Sponsor within 24 hours of site awareness.

Any SAE experienced after this 30-day period should only be reported to the Sponsor if the investigator suspects a causal relationship to the study treatment. Recurrent episodes,

complications, or progression of the initial SAE must be reported as follow-up to the original episode within 24 hours of the investigator receiving the follow-up information.

Information about all SAEs will be recorded on the eCRF. In case of technical difficulties, SAE notification can be carried out by contacting the Contract Research Organization (CRO) OPIS in charge of Pharmacovigilance via email at [contact] or by fax using the following number: [contact].

All SAEs will be followed until satisfactory resolution or until the site investigator deems the event to be chronic or the adherence to be stable. Other supporting documentation of the event may be requested by the study Sponsor and should be provided as soon as possible. The study Sponsor will be responsible for notifying Health Authorities of any unexpected fatal or life-threatening suspected adverse reaction as soon as possible, but in no case later than seven calendar days after the Sponsor's initial receipt of the information.

Suspected Unexpected Serious Adverse Reactions (SUSARs) will be collected and reported to the competent authorities and relevant ethics committees in accordance with Directive 2001/20/EC and as per national regulatory requirements in participating countries.

8.4.7 REPORTING EVENTS TO PARTICIPANTS

Should an event occur that changes the overall benefit/risk ratio of the study, the Sponsor shall evaluate if a risk minimization measure is needed. Should this measure require a substantial amendment to the protocol, the informed consent and patient information will be revised and submitted to the patient for written consent.

8.4.8 EVENTS OF SPECIAL INTEREST

Not applicable.

8.4.9 REPORTING OF PREGNANCY

The investigator shall report all pregnancy exposure occurring in a female patient or in a male patient's partner within 24 hours to the Sponsor using the Pregnancy Reporting Form of the eCRF. In case of technical difficulties, pregnancy notification can be carried out by contacting the Contract Research Organization (CRO) OPIS in charge of Pharmacovigilance via email at [contact] or by fax using the following number: [contact]. The investigator should counsel the subject; discuss the risks of continuing with the pregnancy and the possible effects on the fetus. Monitoring of the subject should continue until conclusion of the pregnancy.

9 STATISTICAL CONSIDERATIONS

9.1 STATISTICAL HYPOTHESES

The primary objective of the trial is to demonstrate the non-inferiority of combined levofloxacin + dexamethasone for 7 days followed by dexamethasone alone for an additional 7 days vs. standard treatment tobramycin + dexamethasone for 14 days in the prevention and treatment of postoperative ocular inflammation and prevention of infection.

The primary endpoint is the proportion of patients without signs of anterior chamber inflammation (sum of cells and flare score = 0) after 14 days of treatment. The following non-inferiority hypotheses will be tested:

 $H_0: \boldsymbol{\pi}_T - \boldsymbol{\pi}_S \leq \textbf{-} \Delta$

 $H_1: \boldsymbol{\pi}_T - \boldsymbol{\pi}_S > \textbf{-} \Delta$

Where π_T and π_S are the proportions of patients without signs of anterior chamber inflammation in the test and standard treatments, respectively, and the non-inferiority margin is $\Delta = 10\%$.

Secondary endpoints:

- Incidence of endophthalmitis
- Proportion of patients without signs of anterior ocular chamber inflammation after 3 and 7 days of treatment
- Conjunctival hyperemia after 3, 7 and 14 days of treatment
- Total Ocular Symptoms Score (TOSS) after 3, 7 and 14 days of treatment
- Ocular pain/discomfort after 3, 7 and 14 days of treatment
- Use of rescue therapy during treatment

No formal statistical hypotheses will be tested for the secondary endpoints.

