2 INTRODUCTION

2.1 STUDY RATIONALE

In clinical practice, topical treatment following cataract surgery is frequently administered using a combination between an antibiotic and a corticosteroid to promote patient adherence to therapy and to obtain both the prevention of infection and the treatment of post-surgical inflammation. The combination of tobramycin and dexamethasone is among the most widely used combinations, but treatment usually lasts for two or more weeks, sometimes tapering posology over several weeks. This therapeutic strategy may however be inappropriate in terms of preventing the development of bacterial resistance, which is favored by prolonged treatment and the use of sub-therapeutic doses. For this reason, antibiotic treatment should not be prolonged beyond the time necessary for the healing of surgically induced epithelial lesions, and therefore should not last more than a week.

Based on these considerations, a product associating a broad-spectrum antibiotic with a highly effective corticosteroid that can be used for a short period of time (one week) would be of considerable interest.

The combination of levofloxacin and dexamethasone tested in this study is the first combination of a quinolone and a steroid under development and represents a major step forward in this direction. Levofloxacin 0.5% + dexamethasone 0.1% ophthalmic solution is an antibiotic/anti-inflammatory combination indicated for the treatment of inflammatory ocular conditions, where bacterial ocular infection or a risk of bacterial ocular infection exists. The active components of this combination are currently available in marketed ophthalmic products.

The purpose of this study is to evaluate the efficacy of a combination between levofloxacin and dexamethasone by demonstrating that the short-term use of this combination for a limited time of one week, followed by treatment with dexamethasone alone, is not inferior to longer treatment with tobramycin + dexamethasone in reducing the incidence of post-operative inflammation/infections while limiting emergence of antibiotic resistance.

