The combination of levofloxacin 5 mg/ml and dexamethasone 1 mg/ml is a new fixed dose combination of an antibiotic, levofloxacin 5 mg/ml, and a corticosteroid, dexamethasone sodium phosphate, corresponding to dexamethasone 1 mg/ml.

The concentration of dexamethasone (1 mg/ml) is well established in ophthalmic solutions both as sole active ingredient and in combination with an antibiotic (e.g. tobramycin) to prevent ocular inflammation following cataract surgery. The penetration of this agent from 0.1% solutions in the aqueous humor is adequate to exert its potent anti-inflammatory activity at the site of action.³³ The dexamethasone 21-phosphate salt is freely soluble in water, allowing its use in water solution. The solution does not require shaking before application and guarantees homogeneity of content of the active ingredient at each application.

Dexamethasone is considered the gold standard in the management of postoperative ocular inflammation and constitutes the reference treatment of controlled studies on new drugs or treatments in development.

The pharmacokinetics of both levofloxacin and dexamethasone confirm that after application to the eye in the form of eye drop solution, both active drugs reach high concentrations in the aqueous humor, with a peak of aqueous levels between 90 and 150 minutes, and detectable concentrations after 12 hours from dosing.³³⁻³⁸ Conversely, the concentrations in plasma are negligible, guaranteeing a lack of systemic effects at least during the short course treatment in this study. The best dosage schedule indicated in literature on the pharmacokinetics of both ingredients is every 6 hours.^{24, 39}

The purpose of this study is to demonstrate that the use of a combination of levofloxacin and dexamethasone for a limited time of one week, followed by treatment with corticosteroid alone, is not inferior in preventing or reducing post-operative inflammation and preventing post-operative infections as compared to a two-week treatment with a combination of tobramycin and dexamethasone, while being in line with the most recent guidelines issued by scientific societies and health organizations in terms of preventing antibiotic resistance.

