4.2 SCIENTIFIC RATIONALE FOR STUDY DESIGN

The combination of tobramycin and dexamethasone has been chosen as control treatment since it is the most commonly used fixed combination in ophthalmology in both Europe and the U.S. As the primary efficacy endpoint of the study is related to the prevention and resolution of ocular inflammation, and given that the anti-inflammatory component of the test and control combinations is the same (dexamethasone 1 mg/ml), a non-inferiority design was deemed appropriate for this study. In fact, the study aims to demonstrate that levofloxacin 5 mg/ml + dexamethasone 1 mg/ml eye drops is at least as effective as the control treatment in terms of anti-inflammatory effect, while offering significant advantages such as the possibility of administering a proven, effective, broad-spectrum antibiotic for a shorter treatment period, thereby reducing the risk of developing antibiotic resistance.

A blinded-assessor design was chosen because particularly suitable for studies involving the topical administration of the drug to be tested when a double-blinded design is not feasible. Furthermore, compared to the double-dummy methodology, the blinded-assessor design has the advantage of not having to administer both active drug and placebo, which can cause dilution of the active test drug or control and an increase of clearance from the site of action.

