9.2 SAMPLE SIZE DETERMINATION

The study plans to enroll 800 patients: 400 patients will be assigned to the test treatment and 400 to standard treatment.

A sample size of 362 patients in each group is required to assess the non-inferiority of the test treatment vs. the standard therapy (i.e. lower limit of the 95% Confident Interval of the difference in proportions, $\pi_T - \pi_S > -0.10$) with 80% power and by applying a two-group large-sample normal approximation test of proportions with a one-sided 0.025 significance level, assuming that the expected difference in proportions is 0 and the proportion in the standard group is 0.64.⁴⁷

The total sample size (362 + 362 = 724) is adjusted to 800 patients considering an expected dropout rate of about 10% using Freedman's formula⁴⁸: n'= 100*n/100-x, where x is the expected dropout rate.

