9.4.2 ANALYSIS OF THE PRIMARY EFFICACY ENDPOINT(S)

The proportion of patients without signs of anterior chamber inflammation (sum of cells and flare score = 0) after 14 days of treatment will be calculated to evaluate the non-inferiority of the test

treatment vs. the standard therapy. Non-inferiority will be assessed by computing the two-tailed 95% confidence interval (CI) of the difference between the two proportions $\pi_T - \pi_S$. Non-inferiority is met if the 95% CI does not cross the predefined non-inferiority margin $\Delta = -0.10$ and lies entirely to the right of the margin (i.e. non-inferiority will be demonstrated if the lower bound of the two-sided 95% CI of the difference is > -0,10).

If the 95% CI of the difference lies completely to the right of 0, the test treatment can be considered more effective than the standard treatment at a 5% significance level.

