9.4.3 ANALYSIS OF THE SECONDARY ENDPOINT(S)

Descriptive statistics and two-sided 95% CIs of the difference between treatments will be computed for the following secondary endpoints:

- Incidence of endophthalmitis
- Proportion of patients without signs of anterior chamber inflammation (sum of cells and flare score = 0) after 3 and 7 days of treatment
- Proportion of patients with conjunctival hyperemia score equal to 0 after 3, 7 and 14 days of treatment
- Proportion of patients with TOSS score equal to 0 after 3, 7 e 14 days of treatment
- Proportion of patients with ocular pain/discomfort score equal to 0 after 3, 7 and 14 days of treatment
- Proportion of patients using rescue therapy during treatment

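### The primary objective claims non-inferiority on prevention of infection, but every confirmatory element of the plan tests anterior chamber inflammation only

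*Combined protocol and SAP*

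**What the plan says.** **The objective includes infection.** Section 9.1 gives the primary objective as non-inferiority "in the prevention and treatment of postoperative ocular inflammation and prevention of infection". The efficacy objective in the synopsis and in Section 3 has the same scope. The purpose statements agree. Section 2.1 aims to show that the short regimen "is not inferior to longer treatment with tobramycin + dexamethasone in reducing the incidence of post-operative inflammation/infections", and Section 2.2 that it "is not inferior in preventing or reducing post-operative inflammation and preventing post-operative infections". The synopsis rationale also names prevention of post-operative infection.

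**The confirmatory elements do not.** H0, H1 and the 10% margin in Section 9.1 are defined on the proportion without signs of anterior chamber inflammation. Section 9.2 sizes the trial "assuming that the expected difference in proportions is 0 and the proportion in the standard group is 0.64", which is that same proportion. Section 9.4.2 sets the rule on it: "non-inferiority will be demonstrated if the lower bound of the two-sided 95% CI of the difference is > -0,10".

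**Infection is secondary.** Incidence of endophthalmitis heads the list of secondary endpoints. Section 9.1 says of that list: "No formal statistical hypotheses will be tested for the secondary endpoints". Section 9.4.3 adds: "Descriptive statistics and two-sided 95% CIs of the difference between treatments will be computed for the following secondary endpoints". No margin is given.

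**The design rationale is narrower.** Section 4.2 says the aim is to show that the test product is "at least as effective as the control treatment in terms of anti-inflammatory effect". It justifies the non-inferiority design by the dexamethasone concentration that the two combinations share.

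**The concern.** An objective labelled primary has two parts, and only one has a hypothesis, a margin and a decision rule. Section 9.4.2 speaks of non-inferiority of the test treatment without limiting it to inflammation. A positive result could therefore be reported as meeting the objective in Section 9.1, infection included, although infection was never tested.

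Inflammation cannot stand in for infection here. The argument in Section 4.2 rests on the common steroid, but the arms differ in antibiotic (levofloxacin or tobramycin) and in its duration (7 or 14 days). Infection is where a difference between the regimens would most need its own evidence. At stake is the scope of the conclusion, not the validity of the inflammation test.

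**Working it through.** **1. Reproduce the plan's sample size.** Inputs from Section 9.2: p = 0.64 in both arms, margin 0.10, one-sided 0.025, power 80%.

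n per arm = 2p(1−p)(1.960 + 0.842)² / margin² = 2 × 0.64 × 0.36 × 7.849 / 0.01 = 361.7, so 362.

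This matches the plan. The size comes from the inflammation inputs alone.

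**2. Expected endophthalmitis cases.** Section 2.2 gives an incidence of 0.03% to 0.3%. Planned enrolment is 800, or 400 per arm.

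- 800 × 0.0003 = 0.24 cases; 800 × 0.003 = 2.4 cases, both arms together.
- Chance of no case in the whole trial: (1 − 0.0003)^800 = 79%; (1 − 0.003)^800 = 9%.

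These counts apply the full background rate, although scheduled assessment ends at Day 15. If anything they are generous.

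**3. What the interval could exclude.** With 0/400 in an arm, the Wilson upper limit is z²/(n + z²) = 3.841/403.841 = 0.951%. With 0/400 in both arms, the Newcombe 95% interval for the difference is therefore −0.95 to +0.95 points.

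- Against 0.3%: 0.951/0.3 = 3.2 times the background rate.
- Against 0.03%: 0.951/0.03 = 31.7 times.

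One case in one arm and none in the other (1/400 vs 0/400) gives −0.72 to +1.40 points. A plain normal-approximation interval is no help with no cases: its standard error is 0, so it collapses to [0, 0].

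**4. Size needed under assumed margins (illustration only).** The documents give no infection margin, so a range is shown. The formula, alpha and power are those of step 1.

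| Background rate | Assumed margin (points) | Margin ÷ rate | n per arm |
|---|---|---|---|
| 0.3% | 0.3 | 1 | 5,217 |
| 0.3% | 0.5 | 1.7 | 1,879 |
| 0.3% | 1 | 3.3 | 470 |
| 0.03% | 0.03 | 1 | 52,311 |
| 0.03% | 1 | 33 | 48 |

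For example, 2 × 0.003 × 0.997 × 7.849 / 0.003² = 5,217. The normal approximation is poor at such counts. The first row has only about 16 expected cases per arm (5,217 × 0.003), and the last has almost none. The table shows orders of magnitude and is not a proposed design. Of these cases, only the last fits within 400 per arm, and there the margin is over 30 times the background rate.

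**The case against.** **The analysis sections already treat infection descriptively.** Section 9.1 lists endophthalmitis as secondary and disclaims formal tests, and Section 9.4.3 prescribes descriptive statistics with an interval. H0 and H1 name anterior chamber inflammation explicitly. A careful reader would see that infection is not tested. This stands, and it makes the problem one of the objective's scope rather than of the analysis. It does not close the gap, because no section takes infection out of the objective that Section 9.1 calls primary.

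**No section says that a positive inflammation result proves non-inferiority on infection.** Correct. A reader might infer that the plan makes this claim outright, and the documents do not support that. What they leave open is the inference, through an unrestricted objective and an unqualified decision rule.

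**Section 4.2 is not a rival objective.** It explains why non-inferiority suits the primary endpoint, and it refers to anti-inflammatory effect rather than to the anterior chamber. It shows a narrower intent but does not formally contradict Section 9.1.

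**Infection is monitored in other ways.** The visits in Section 8.1 include a check for any ocular infection, and rescue therapy (Section 6.5.2) covers infection. Neither gives a non-inferiority test. However, the documents give no rate for infections other than endophthalmitis, so the figures above cannot be extended to them.

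**Follow-up is not as short as Day 15 suggests.** A reader might infer that the trial would miss most endophthalmitis. Section 2.2 says that cases usually appear in the first days and that 80% have developed by six weeks. Section 8.4.4 records serious adverse events for 30 days after participation, to about Day 45. Serious late cases should therefore be reported, though without a scheduled examination. The main limit is rarity, not the visit schedule.

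**Conclusion.** The concern holds as a mismatch between the stated primary objective and what is tested. The objective includes prevention of infection, while the hypotheses, margin, sample size and success rule concern inflammation only.

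For endophthalmitis, 800 patients cannot support a non-inferiority conclusion at any margin close to the background rate: 0.24 to 2.4 expected cases, and ±0.95 points even with no case in either arm. This rests on the protocol's own incidence range, equal arms and all 800 patients being assessed. The sample sizes in the table rest on assumed margins as well.

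A reader might conclude that the trial is underpowered or that its sample size is wrong. The documents do not support that: 362 per arm reproduces exactly for the endpoint it was built on, and the inflammation analysis stands. The change should be made because it decides what a positive trial may be said to have shown.

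**What to change.** 1. In Section 9.1, Section 3 and the synopsis objective, limit the non-inferiority objective to postoperative ocular inflammation as measured by the primary endpoint. Make infection (endophthalmitis) a secondary descriptive objective, and state that no non-inferiority conclusion on infection will be drawn.
2. Align the purpose statements in the synopsis rationale, Section 2.1 and Section 2.2.
3. Report the endophthalmitis difference with an exact or score 95% interval, unless the statistical analysis plan to which Section 9.3 refers already names a method valid for zero counts. Section 9.4.3 names none.
4. List separately any endophthalmitis reported as a serious adverse event after Day 15.

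**Cost:** changes of wording, one named interval method and one listing, with no extra patients or visits. The sponsor gives up the infection part of the non-inferiority claim. The listing of later cases may be incomplete, because it depends on safety reporting rather than on a scheduled examination.
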